The primary goal of this study is to test the effectiveness of instituting an Epic BPA in increasing Maryland Quit Line referrals. The secondary goals are to measure the BPA's effect and the effect of additional provider education on patient engagement with the Quit Line, and on prescription of medications that aid in smoking cessation. A third goal is to obtain initial provider feedback on the BPA to inform roll-out of this BPA across the health system.

Aim 1: In a three-arm, cluster randomized trial, to test the effectiveness of an Epic BPA with provider educational support and provider detailing in provision of smoking cessation services.

Hypothesis 1: An Epic-based BPA to prompt providers to electronically refer people who are ready to quit smoking to the Maryland Quit Line will increase use of this service compared to waitlist control.

Hypothesis 2: An Epic-based BPA supplemented with educational materials and academic detailing will increase Quit-Line referral compared to control.

Hypothesis 3: Additional provider support including educational materials, in-person academic detailing, will increase successful referrals to the Quit Line and prescription of cessation pharmacotherapy compared to waitlist control and BPA only

3. Background

Smoking remains the number one cause of preventable death in the United Sates. Despite decades of declining rates of smoking, the burden of disease caused by smoking remains high. ¹ 22.2% of adults in the U.S. smoke, and 18.4% smoke daily. ² This issue remains a difficult but potentially high-yield area of medicine to improve health outcomes by improving implementation of behavioral and medical therapies. Though phone-based smoking cessation counseling has been shown to be beneficial in improving quit rates³, physicians do not regularly refer their patients for this intervention. There is no decision support tool or automatic referral mechanism embedded in the EMR used at Johns Hopkins. EMR based-interventions have been shown change provider behavior to increase quit line referrals in the outpatient setting ⁴ and the inpatient setting. ⁵ And while prompts embedded in EMRs modestly increase documentation of tobacco use and referral to counseling, more research is needed in this area to improve the effectiveness of these prompts. ⁶ Thus we see an opportunity to institute interventions that is aimed at changing provider behavior and improving patient care.

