Based on prior research with a comparable tool used in the inpatient setting where compared to control arm physicians, intervention physicians were more likely to order tobacco treatment medication (24% v. 9%, P = 0.0001, Fisher's exact test), and make a referral to the state smokers' quitline (19% v. 0%, P < 0.0001, we expect a 20% absolute increase in the percentage of the population of active smokers who are referred to the Quit Line among providers that receive the BPA, and a 30% increase among providers receiving the BPA + educational materials/detailing, compared to the control condition. Our main outcome, is quitline referral, which is a dichotomous outcome. We will use logistic regression accounting for clustering by site and provider to determine the difference in quit-line referral between the BPA only arm, and the waitlist control (B vs C), the BPA + education and the waitlist control (A vs C), and the BPA + educational materials arm and the BPA only arm (A vs B). The two primary testing contrasts will be B vs C and A vs C, each will be evaluated at type I error of 0.025 to safeguard the overall type I error for testing the 2 primary contrasts. The secondary contrast of A vs B is exploratory in nature, to estimate the potential incremental increase in quitline referral with additional provider education. The difference in % referral between arms and its corresponding 95% CI will be calculated. Due to the design of cluster randomization by sites, provider level and patient level characteristics that are not balanced by randomization between arms will be adjusted for in the logistic regression model.

In this 3-arm trial, we expect 7 JHCP sites per arm, with an average cluster size of 1000 smokers per site (based on current patient numbers in the clinics, number of smokers, and proportion willing to quit). Assuming intracluster correlation of 0.1, and a 5% quitline referral in the control Arm C, we will have 88.6% power to detect a 20% absolute increase in quitline referral in Arm B when testing the contrast of B vs C using a Z-test at type I error of 0.025, and 99.4% power to detect a 30% absolute increase in quitline referral in Arm A when testing the contrast of A vs C using a Z-test at type I error of 0.025.

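### Holm's step-down in place of the fixed 0.025 split would raise B vs C power from about 88% to 93% at the same 5% family-wise error (optional improvement)

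*Combined protocol and SAP*

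**What the plan says.** Section 7c (statistical plan) defines the primary family: "The two primary testing contrasts will be B vs C and A vs C". On error control it says that "each will be evaluated at type I error of 0.025 to safeguard the overall type I error for testing the 2 primary contrasts". A vs B is exploratory and outside the family. Neither section 7c nor any other part of the document gives a step-down, hierarchical or alpha-recycling rule.

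The power statement in the same section assumes that "we expect 7 JHCP sites per arm, with an average cluster size of 1000 smokers per site", with an intracluster correlation of 0.1 and 5% referral in Arm C. For a 20-point increase in Arm B it reports 88.6% power; the test is specified by the words "when testing the contrast of B vs C using a Z-test at type I error of 0.025". For the other primary contrast the stated figure is "99.4% power to detect a 30% absolute increase in quitline referral in Arm A when testing the contrast of A vs C". It does not say whether 0.025 is one-sided or two-sided.

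On estimation, section 7c says: "The difference in % referral between arms and its corresponding 95% CI will be calculated". It does not name the contrasts or relate the interval level to the test level. I read the sentence as covering all three contrasts.

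Section 2 (Objectives) gives the primary goal as "to test the effectiveness of instituting an Epic BPA in increasing Maryland Quit Line referrals". Hypothesis 1 is that the BPA "will increase use of this service compared to waitlist control". B vs C is the contrast that answers this.

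**The concern.** The fixed split spends 0.025 on each contrast whatever happens to the other. If A vs C is rejected, the 0.025 reserved for it could be passed to B vs C without raising the family-wise error above 5%, and the plan leaves it unused. Since the plan expects A vs C to succeed with 99.4% power, under its own assumptions B vs C could almost always be tested at 0.05. B vs C answers the primary goal and has the lower power, so the lost power falls where it matters most.

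A smaller point concerns reporting. With 0.025 tests and 95% intervals side by side and no explanation, a reader could see an interval for B vs C that excludes zero next to a test that failed.

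**Working it through.** **Inputs (section 7c).** 7 sites per arm; 1000 smokers per site; intracluster correlation 0.1; referral 5% (C), 25% (B), 35% (A); Z-test at 0.025 per contrast.

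**Step 1: effective sample size.** Design effect = 1 + (1000 − 1) × 0.1 = 100.9. Effective n per arm = 7 × 1000 / 100.9 = 69.4.

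**Step 2: reproduce the plan's power.** With unpooled variance, SE = √[(p₁(1−p₁) + p₂(1−p₂)) / n] and power = Φ(difference/SE − critical value). The two-sided 0.025 critical value is 2.241.

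- B vs C: SE = √[(0.0475 + 0.1875)/69.4] = 0.0582; 0.20/0.0582 − 2.241 = 1.195; power 88.4% (plan: 88.6%).
- A vs C: SE = √[(0.0475 + 0.2275)/69.4] = 0.0630; 0.30/0.0630 − 2.241 = 2.52; power 99.4% (plan: 99.4%).

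Rounding effective n up to 70 gives 88.7% for B vs C, so the printed 88.6% is a matter of rounding. A one-sided 0.025 test would give 93.0%, so the plan's figure implies a two-sided test.

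**Step 3: Holm.** B vs C is rejected if its p-value is at most 0.025, or if A vs C passes at 0.025 and the B vs C p-value is at most 0.05. The two statistics share Arm C (correlation 0.19), so I simulated the three arm means, with 4 million draws.

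| Planned effects | Fixed 0.025 | Holm |
|---|---|---|
| B vs C | 88.4% | 93.0% |
| A vs C | 99.4% | 99.7% |
| Both | 88.0% | 92.8% |

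The ceiling for B vs C, a test always at two-sided 0.05, is Φ(0.20/0.0582 − 1.960) = 93.0%, so Holm recovers nearly all of it. With 8 sites per arm, the fixed split gives 92.4%.

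**Step 4: error rates.**

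- All arms at 5%: family-wise error 4.6% under either procedure.
- A effective (35%), B null: B vs C error 2.5% (fixed), 5.0% (Holm).
- B effective (25%), A null: A vs C error 2.5% (fixed), 4.6% (Holm).

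Holm stays within 5% throughout.

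**Step 5: sensitivity of B vs C power.**

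| Scenario | Fixed | Holm |
|---|---|---|
| Effects of 15 and 25 points (my assumption) | 69.2% | 78.0% |
| B 25%, A 25% | 88.4% | 92.2% |
| B 25%, A 20% | 88.4% | 91.1% |
| B 25%, A 5% (no effect) | 88.4% | 88.5% |
| Planned effects, 11 sites per arm | 98.1% | 99.1% |

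With a site-level t reference on 12 degrees of freedom (14 sites in two arms), B vs C power is 79.6% at 0.025 and 88.3% at 0.05. Absolute power is lower, and the difference between the two levels is larger.

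**Step 6: test against interval, B vs C.** Under the fixed split, the 0.025 test and a 95% interval disagree when the observed difference lies between 1.960 × 0.0582 = 11.4 points and 2.241 × 0.0582 = 13.0 points. Under planned effects the chance of disagreement is:

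- fixed 0.025 with a 95% interval: 4.6%;
- Holm with a 95% interval: 0.05%;
- Holm with a 97.5% interval: 4.6%.

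If Arm A has no effect, Holm and the 95% interval disagree in about 4.5% of trials.

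**The case against.** The strongest reply is that nothing is broken. The plan pre-specifies two contrasts, controls the overall error and marks the third contrast as exploratory. It also states adequate power and sets no power target that it misses. That is correct, and it is why the point is optional.

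Five further arguments stand as limits on the advice:

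- **Holm is better for rejections only.** The fixed split has a simple matching interval (97.5%); Holm has no fixed-level interval that always agrees with its decision. A sponsor who puts estimation first, or who wants the stricter B vs C test in case only the education package works, could reasonably keep the split.
- **The gain depends on Arm A.** The inpatient study cited in section 7c reports 19% vs 0% quitline referral, and no source is given for the further 10 points expected in Arm A. A weaker Arm A means a smaller gain.
- **The site count is unsettled.** The abstract and the study population paragraph in section 4a give 22 sites; the section 4a overview gives 35. With about 11 sites per arm (35/3 = 11.7), the gain is only 1 point.
- **The 93.0% is a large-sample figure.** With few sites, absolute power would be lower, as the t reference shows. The case for Holm does not weaken.
- **Timing.** Section 4a describes the academic detailing in the past tense, so delivery was under way or finished when this version was written. The document does not say whether outcomes had been seen. Relaxing a threshold after seeing them would not be acceptable.

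The interval point is minor: an unadjusted 95% interval contradicts nothing, and the tests are the decision rule.

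**Conclusion.** The point holds as an optional efficiency gain; the plan contains no error here. Holm's advantage in rejections follows from its definition and does not depend on the assumed effects. Its size does. The gain is 4.6 points for B vs C under the plan's assumptions, more if both effects are 5 points smaller than planned, and close to nothing if Arm A has no effect or if there are many more sites. The figures rest on the large-sample, unpooled, two-sided Z-test that reproduces the plan's own power. Both the two-sided reading and the 5% family-wise level (2 × 0.025) are inferred, as the plan states neither.

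**What to change.** **Preferred.** In section 7c, replace the fixed split with Holm: smaller p-value against 0.025 and, if it passes, the other against 0.05. Report Holm-adjusted p-values. Keep the 95% intervals, label them as not adjusted for multiplicity, and state that the Holm test governs the conclusion.

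**Alternative.** Keep the fixed 0.025 tests and report 97.5% intervals for B vs C and A vs C, with 95% for exploratory A vs B. The two primary intervals become 14% wider (2.241/1.960 = 1.14).

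Do not combine Holm with 97.5% intervals. In either case, state that 0.025 is two-sided and name the contrasts that the intervals cover. Agreement between test and interval is approximate in any case, because the test comes from a logistic model and the interval is for a difference in percentages.

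**Cost.** Two or three sentences, with no added sites or data. Adopt Holm only if the change is dated and documented before anyone sees outcomes by arm. If that is no longer possible, keep the fixed split and use the alternative.

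### The two primary contrasts are each tested at 0.025, but the only interval planned for the difference in referral is a 95% CI, which matches a 0.05 test

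*Combined protocol and SAP*

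**What the plan says.** All of the relevant text is in section 7c (statistical plan including sample size justification) of the combined protocol and SAP.

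- Primary contrasts: "The two primary testing contrasts will be B vs C and A vs C".
- Error control: "each will be evaluated at type I error of 0.025 to safeguard the overall type I error for testing the 2 primary contrasts".
- Third comparison: "The secondary contrast of A vs B is exploratory in nature".
- Model: "We will use logistic regression accounting for clustering by site and provider to determine the difference in quit-line referral".
- Interval: "The difference in % referral between arms and its corresponding 95% CI will be calculated". No other confidence level is given for any contrast, and these intervals are not labelled as descriptive or unadjusted.
- Power: 88.6% for B vs C and 99.4% for A vs C, each for a Z-test at type I error 0.025. Whether the tests are one-sided or two-sided is not stated in words.

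**The concern.** A confidence interval and a test agree when the confidence level is one minus the two-sided significance level. A two-sided test at 0.025 pairs with a 97.5% interval; a 95% interval pairs with a test at 0.05. The plan halves the error rate for the two primary tests and then reports the effect at the unhalved level.

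This matters because the difference in percentage referred is the scale on which the plan states its expected effects and its power, so readers will look at it first. A 95% CI that excludes zero next to a primary test that is not significant invites the claim that the contrast succeeded. If readers use both intervals that way, the protection that the split was meant to give is lost.

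**Working it through.** **Inputs (all from section 7c).** 7 sites per arm, 1000 smokers per site, intracluster correlation 0.1, control referral 5%, Arm B 25%, Arm A 35%, type I error 0.025 per contrast.

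**1. Reproduce the stated power and settle the sidedness.**
- Design effect = 1 + (1000 − 1) × 0.1 = 100.9.
- Effective sample size per arm = 7000 / 100.9 = 69.4.
- Standard error with unpooled variance = √[(p₁(1 − p₁) + p₂(1 − p₂)) / 69.4].
  - B vs C: √[(0.0475 + 0.1875) / 69.4] = 0.0582, or 5.82 points.
  - A vs C: √[(0.0475 + 0.2275) / 69.4] = 0.0630, or 6.30 points.
- Power = Φ(difference / SE − critical value).

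| Contrast | Difference / SE | Two-sided 0.025 (critical value 2.241) | One-sided 0.025 (critical value 1.960) | Plan states |
|---|---|---|---|---|
| B vs C | 3.436 | 88.4% | 93.0% | 88.6% |
| A vs C | 4.765 | 99.4% | 99.7% | 99.4% |

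B vs C is the contrast that discriminates. With pooled variance it gives 86.5% two-sided and 91.8% one-sided. Neither one-sided figure is close to 88.6%, so the plan was powered at two-sided 0.025.

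**2. Compare the interval levels.** A 95% CI uses 1.960 and a 97.5% CI uses 2.241. The ratio is 2.241 / 1.960 = 1.144, so the matching interval is 14.4% wider.

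| Contrast at design rates | 95% half-width | 97.5% half-width |
|---|---|---|
| B vs C | 1.960 × 5.82 = 11.4 points | 2.241 × 5.82 = 13.0 points |
| A vs C | 1.960 × 6.30 = 12.3 points | 2.241 × 6.30 = 14.1 points |

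**3. Find the observed differences where the interval and the test disagree.** The standard error must be taken at the observed rates, because it shrinks as the treated rate falls towards 5%. With 5% in control and effective n of 69.4 per arm:

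| Observed | Difference (points) | z | 95% lower limit (points) | 97.5% lower limit (points) |
|---|---|---|---|---|
| 14% vs 5% | 9 | 1.83 | −0.6 | −2.0 |
| 15% vs 5% | 10 | 1.99 | +0.2 | −1.3 |
| 16% vs 5% | 11 | 2.15 | +1.0 | −0.5 |
| 17% vs 5% | 12 | 2.30 | +1.8 | +0.3 |

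Solving for z = 1.960 and z = 2.241 gives differences of 9.8 and 11.6 points. Between them the 95% CI excludes zero and the test at 0.025 fails.

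**4. How often this happens.** The chance that z falls between 1.960 and 2.241 is Φ(2.241 − δ) − Φ(1.960 − δ), where δ is the true difference divided by its SE. It is 4.6% at the assumed B vs C effect, 0.3% at the assumed A vs C effect, and about 11% if the true difference is 10 to 12 points.

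**5. Familywise error if both intervals are read as tests.** The two contrasts share Arm C, so with equal arms their test statistics have correlation 0.5 under the null. The probability that at least one exceeds the critical value in absolute size is 9.1% at 1.960 and 4.6% at 2.241. Ignoring the correlation, the figures are 1 − 0.95² = 9.75% and 1 − 0.975² = 4.9%.

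**The case against.** The strongest reply is that the decision rule is already fixed by the tests. Section 7c does not make the interval a decision rule and does not call the intervals simultaneous. Each 95% CI keeps its own nominal coverage, and reporting conventional 95% intervals beside a Bonferroni-type test is common practice. This stands in part: the primary tests are unaffected, and 95% intervals would be acceptable if labelled unadjusted. The plan does not label them so, and it gives no interval at the level it tests.

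A second reply is that the interval sentence directly follows the one on A vs B, for which 95% is reasonable. Its wording covers differences between arms in general, however. If it did apply to A vs B alone, the primary contrasts would have no planned interval at all.

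Three stronger readings are tempting and should not be drawn.

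- A reader might infer that the interval will be computed from raw proportions, ignoring clustering, and so be far too narrow. The plan does not prescribe that. It says the clustered logistic regression will be used to determine the difference in referral. What is missing is only the step from the model's odds ratios to a difference in percentages.
- A reader might take the two B vs C half-widths, 11.4 and 13.0 points, as the range of disagreement. They rest on the standard error at 25% vs 5%. An observed 12 points against 5% gives z = 2.30 and p = 0.021, which passes at 0.025.
- A reader might conclude that the primary tests have inflated error. They do not; the inflation arises only if the 95% intervals are used in their place.

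**Conclusion.** The point holds as a minor mismatch between the planned interval and the planned test. The primary contrasts are tested at two-sided 0.025, and the only planned interval corresponds to 0.05. An observed difference of about 9.8 to 11.6 points would give conflicting messages, and reading both intervals as tests would put familywise error at about 9.1% instead of 4.6%.

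Two-sided testing is inferred from the stated power, since the plan does not say. The window assumes 5% observed referral in control, the plan's 7 × 1000 per arm, an intracluster correlation of 0.1 and a Z approximation on the difference scale; other control rates or correlations would move it. The familywise figures depend only on equal arms with a shared control.

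**What to change.** In section 7c, replace the interval sentence with wording such as: For B vs C and A vs C, the difference in percentage referred will be reported with a 97.5% CI, derived from the same clustered logistic model as the test (for example by marginal standardisation with a variance that accounts for clustering); the exploratory A vs B difference will be reported with a 95% CI. Add that the primary tests are two-sided at 0.025.

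If the team prefers to keep 95% intervals for the primary contrasts, it should label them unadjusted and descriptive and say that conclusions rest on the tests at 0.025.

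The cost is wording only. Primary intervals become about 14% wider, and the tests, sample size and conduct do not change. Because the test is on the log-odds scale and the interval on the difference scale, slight disagreement at the boundary could remain, but the mismatch in level would be gone.

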Recruitment: All JHCP sites that provide adult primary care will be included. Providers (physicians and office health professionals like CMAs) will be the target of the intervention. Patients will not directly know about the study but there will be a smoking cessation handout available at each office if patients are interested.

Consent: Because this is an evaluation of an EMR intervention, looking at outcomes in aggregate only, not by provider or by patient, we are applying for a waiver of consent.

Randomization: Randomization to one of the three clusters will occur at the level of each JHCP site. Sites will be stratified by size and a randomization sequence will be generated by an online random number generator.

Intervention: There are several components to the intervention:

- 1. **BPA**: The BPA is an Epic prompt that fires when a provider opens an encounter with a patient who is actively smoking. Providers will be asked to assess smoking cessation readiness and to refer patients to the free Maryland Quit Line if the patient is receptive. The Quit Line will receive an electronic referral with the patient's details. A Quit Line certified smoking cessation counselor will then call the patient at a later date and provide counseling. Receptive patient will receive up to four calls. They will receive counseling from a trained quit coach and be offered free access to NRT.
- 2. **Quit Line**: This free telephone-based counseling service is offered to smoker in Maryland. Services offered include on-the-phone smoking cessation counseling and free nicotine replacement.
- 3. **Consolidated educational hand out**: A one-page hand out will be sent to providers electronically for quick reference. The hand out will include a summarization of counseling, pharmacotherapy, cessation referrals, and coding for cessation counseling.
- 4. **Online modules**: Providers will be directed to optional, self-paced educational modules. The Maryland HABITS program is a series of online modules that include general concepts in smoking cessation, pharmacotherapy, and counseling skills. The modules are text and video based and can be completed in about one hour. Providers can also watch example videos of interviews using these skills.

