Control: JHCP sites randomized to Arm C will receive no intervention, serving as controls for the first 6 months of the trial period. After six months, Arm C will be randomized to receive either the Epic BPA or the BPA + education..

Measures:

	Outcome	How outcome is measured	
Primary outcome	Provider electronic referrals to the Maryland Quit line	Orders are tracked though Epic	
Secondary outcomes	Patient prescribed nicotine replacement, bupropion, or varenicline	Orders are tracked though Epic	
	Patient engagement with Quit Line (number of interactions, use of services)	Maryland Quit Line collects data during encounters and will provide this information to the study group	
	Patient-reported smoking cessation after 1 year	The patient's smoking status as logged in Epic	

Provider feedback on BPA:

We will obtain initial provider feedback on the BPA 6 months after initial roll out. Only providers at sites where the BPA has been implemented will be asked to fill out the survey. We will not collect names, but will collect site (to verify that BPA was active), years in practice and provider type. On the survey we will include the statement that participating in this survey serves as consent to the study. To protect confidentiality, no names or DOB will be collected. Data will be stored on the Johns Hopkins Secure Server and site data will be presented only in aggregate, by cluster (e.g. we will not report on individual sites, but rather by assigned cluster condition).

- b. Study duration and number of study visits required of research participants. Study duration will be 1 year.
- c. Blinding, including justification for blinding or not blinding the trial, if applicable.

Providers will be notified about this implementation study and will know what arm they have been randomized to.

- d. Justification of why participants will not receive routine care or will have current therapy stopped. The control group will receive routine care from their provider, which can include counseling, pharmacotherapy, and Quit Line referral. The study will not prevent any provider from assisting smokers to quit with all guideline-based care.
- e. Justification for inclusion of a placebo or non-treatment group.

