While implementing the BPA to increase electronic referrals to the Quit Line is quite easy since the interface is already built, it is important for the health system to determine the added value of additional training for providers to use this referral effectively. We think a delay of 6 months in the added training does not increase risk beyond expected benefits. In addition, the Maryland State Quit Line will need this time to see if they can handle the increased volume.

To evaluate the effectiveness for the BPA, we feel a control group is needed. Arm B (the educational control) is necessary to evaluate whether the BPA with education is better than a BPA launched alone without education.

- f. Definition of treatment failure or participant removal criteria. Not applicable.
- g. Description of what happens to participants receiving therapy when study ends or if a participant's participation in the study ends prematurely.

 Not applicable.

5. Inclusion/Exclusion Criteria

BPAInclusion criteria: Sites are JHCP primary care practices.

Exclusion criteria: There are no exclusion criteria.

Survey: Providers will be included if they practice at the original sites randomized to either the BPA or the BPA + education

6. Drugs/ Substances/ Devices

- a. The rationale for choosing the drug and dose or for choosing the device to be used. Not applicable.
- b. Justification and safety information if FDA approved drugs will be administered for non-FDA approved indications or if doses or routes of administration or participant populations are changed.

Not applicable.

c. Justification and safety information if non-FDA approved drugs without an IND will be administered.

Not applicable.

Date: _____November 3, 2017

Principal Investigator: [name] MPH

Application Number: **IRB00124880**

7. Study Statistics

a. Primary outcome variable.

• Provider electronic referrals to the Maryland Quit line

- b. Secondary outcome variables.
 - Patient prescribed nicotine replacement, bupropion, or varenicline
 - Patient engagement with Quit Line (number of interactions, use of services)
 - Patient-reported smoking cessation after 1 year
- c. Statistical plan including sample size justification and interim data analysis.

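### The primary model does not name the site-size stratum used in randomisation, and its other covariates are left to be chosen by observed imbalance.

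*Combined protocol and SAP*

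**What the plan says.** Section 4a (Randomization) makes the site the unit of allocation: "Randomization to one of the three clusters will occur at the level of each JHCP site". It then restricts the allocation by size: "Sites will be stratified by size and a randomization sequence will be generated by an online random number generator". Neither the number of strata nor the cut-points are given.

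Section 7c describes the primary model: "We will use logistic regression accounting for clustering by site and provider to determine the difference in quit-line referral". No size term is named. The only statement on covariates is that "provider level and patient level characteristics that are not balanced by randomization between arms will be adjusted for in the logistic regression model". The section lists no candidate characteristics, gives no criterion for imbalance, and sets no date by which the covariate set is fixed. No other section supplies these. The reported estimate comes from the same analysis: "The difference in % referral between arms and its corresponding 95% CI will be calculated".

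The plan is silent on the stratum; it does not exclude it. It also does not say that outcome data will have been seen when covariates are chosen.

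**The concern.** There are two linked gaps.

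**The stratum.** Stratified allocation removes size-related differences between arms from the sampling error of the treatment contrast. The analysis recovers that gain only if it conditions on the stratum. A site random effect or a cluster-robust variance does not do so, because it counts size-related variation between sites as error. The imbalance rule does not help either: it covers provider and patient characteristics, whereas size belongs to the site and is the factor that stratification is meant to balance. If size predicts referral, the standard error is too large.

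**The other covariates.** With no list, criterion or date, two analysts following section 7c could fit different primary models and both be compliant. With about seven sites per arm, chance imbalance in anything that varies between sites is likely, so the choice can affect the estimate.

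**Working it through.** **Inputs from section 7c.** 7 sites per arm, 1000 smokers per site, 5% referral in Arm C, 25% in Arm B and 35% in Arm A (absolute increases of 20 and 30 points), type I error 0.025 per contrast, and the assumption stated as "Assuming intracluster correlation of 0.1, and a 5% quitline referral in the control Arm C".

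**Step 1: reproduce the plan's power.**
- Design effect = 1 + 999 × 0.1 = 100.9.
- SE (B vs C) = √[(0.25×0.75 + 0.05×0.95) × 100.9 / 7000] = √[0.235 × 100.9 / 7000] = 0.0582.
- Two-sided Z-test at 0.025: 88.4% for B vs C (plan: 88.6%) and 99.4% for A vs C (plan: 99.4%).

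The base set-up therefore matches the plan. None of the plan's figures depends on covariates.

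**Step 2: move to a site-level t-test.** With 14 sites and 12 df, the same SE gives 79.6% for B vs C. The drop from 88.4% comes from using t instead of Z and has nothing to do with the stratum. It is the baseline for the comparisons below.

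**Step 3: leave the stratum out.** Assumptions not in the documents: two strata, split 3 and 4 sites in each arm, with the stratum explaining a share R² of between-site variance. Mean binomial variance is 0.235/2 = 0.1175, so between-site variance is 0.1175 × 0.1 = 0.01175 and within-site variance of a site mean is 0.1175 × 0.9/1000 = 0.000106.

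The true error variance of a site mean is 0.01175(1−R²) + 0.000106. A model without the stratum estimates, on average, that quantity plus (14/12) × R² × 0.01175:
- R² = 10%: true 0.01068, estimated 0.01205, so the SE is too large by √(0.01205/0.01068) = 1.06.
- R² = 20%: true 0.00951, estimated 0.01225, so the SE is too large by √(0.01225/0.00951) = 1.13.

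Simulated results for B vs C, without v with the stratum:

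| R² | Type I error | Mean 95% CI width (points) | Power |
|---|---|---|---|
| 0 | 0.025 v 0.025 | – | 79.7% v 78.7% |
| 10% | about 0.019 v 0.025 | 25.1 v 23.8 | 80.0% v 83.0% |
| 20% | 0.013 v 0.025 | 25.3 v 22.4 | 80.5% v 87.4% |

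Coverage of the nominal 95% interval without the stratum is 96.1% and 97.1% at R² of 10% and 20%. Three strata give power of 79.8% v 81.8% and 80.6% v 86.4%.

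**Step 4: cost of site-level terms that explain nothing.** From noncentral t, B vs C power is 79.6% at 12 df, then 78.6%, 77.4%, 75.9% and 73.9% as 1, 2, 3 or 4 df are spent. The break-even R² is 2.2%, 4.9%, 8.1% and 12.1%. This applies to terms balanced between arms. One site-level covariate not balanced by design costs more: power falls from 79.4% to 74.5% at R² = 0, with break-even near R² = 10%.

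**The case against.** The strongest reply is that the stratum affects efficiency, not validity. Leaving it out is conservative, costs nothing if size is unrelated to referral, and no section reports such a relation. This stands, and it limits the weight of the point. The illustration is also simplified: it is a linear model of site means with every site at 1000 smokers, whereas the plan specifies a patient-level logistic model and real sites differ in size. The direction should carry over; the exact figures may not.

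Three stronger readings are tempting, and the documents do not support them.

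- **A reader might infer that the imbalance rule inflates type I error.** In a site-level illustration with three or five candidate covariates, mechanically adjusting for every one with a mean difference above 0.5 SD gave about 0.015, below the nominal 0.025. Only free choice of the most favourable model gave 0.053 or 0.066, and the plan describes no such choice.
- **A reader might infer that the open choice makes the result arbitrary.** With one patient-level covariate explaining 10% or 20% of between-site variance, the significance decision differs between the model with it and the model without it in about 8% or 12% of trials at the planned 20-point effect. About 6 of those 8 points and 10 of those 12 are trials in which only the adjusted model detects the true effect, so most of the disagreement is power gained by adjustment. With no effect the figure is 1.8% or 2.5%. Either model, if fixed in advance, holds type I error at about 0.025.
- **A reader might infer that provider covariates cannot be compared with Arm C, because the provider survey covers only BPA sites** ("Only providers at sites where the BPA has been implemented will be asked to fill out the survey"). The survey is descriptive, and no section links it to the primary model. It says nothing about which provider data that model will use.

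**Conclusion.** The point holds, led by the stratum. The randomisation is stratified by size, the primary model does not name that stratum, and the only covariate rule does not reach it. If size explains 10% to 20% of between-site variance, including it gains about 3 to 7 points of power and shortens the 95% interval by about 1.3 to 2.9 points. If size explains less than about 2%, including it loses up to 1 point of power. These sizes rest on the assumed R², number of strata and split, none of which the documents give.

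The open covariate rule is a gap in specification: the primary model is not fully defined before the data are seen. No inflation of type I error is shown for it when applied mechanically. The trial is not invalidated and no stated figure changes, but the wording should be corrected before outcome data are examined.

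**What to change.** In section 7c:

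1. Add the site-size stratum, as used in the randomisation, to the primary model as a fixed term, and state the strata.
2. Replace selection by observed imbalance with a short, named and dated covariate set, fixed before outcome data are examined. Draw it from characteristics recorded in Epic for all three arms. Include provider characteristics only if they are available in all arms; the documents do not show that they are, so this must be confirmed first.
3. Limit site-level terms to the stratum, or to one or two in total.
4. Keep imbalance-driven adjustment as a sensitivity analysis, with its criterion stated.

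The cost is a wording change plus the degrees of freedom used. If the terms explain nothing, B vs C power falls by about 1 point for one balanced site-level term and 2.2 points for two. A site-level covariate not balanced by design costs about 5 points (79.4% to 74.5%), which is the reason for the limit in item 3.
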